2.7 Dose and Schedule

The type I interferons down-regulate the expression of pro-angiogenic molecules, including bFGF, IL-8, MMP-2 and MMP-9. Systemic chronic administration of IFN- α or IFN- β has been shown to produce regression of vascular tumors by down-regulation of mRNA expression and protein production of the angiogenic factor, bFGF23.

This effect requires long term exposure to IFNs, as has been demonstrated clinically and in vitro. Through in vitro and animal model, Slaton et.al have demonstrated that daily administration of interferon alpha-2a, at doses far below maximally tolerated doses, produced the most significant inhibition of tumor growth, tumor vascularization, and maximal inhibition of angiogenesis-regulating genes. His experiments demonstrated that when human bladder cancer cell lines were implanted into the bladder of mice and the mice were injected subcutaneously daily, 1x/ week or 2x/ week for 4 weeks with interferon alfa-2a. Examination and evaluation after 4 weeks demonstrated that interferon alfa-2a administered daily produced superior anti-proliferative and anti-angiogenic activities compared to an equivalent weekly dose administered 1, 2 or 3 X/week.

In a comparison of escalating daily doses of interferon alfa-2-a (2500-50,000 units/dose), maximal inhibition occurred at a dose of 5000 or 10,000 units/day. Administration of higher doses failed to produce significant anti-angiogenic effects. [18]

2.7.1 Doses for Pegylated interferon

-For patients with chronic hepatitis as a monotherapy the dose is 1 mcg/kg/Week SC x1 year.

-For patients with melanoma with microscopic or gross nodal involvement within 84 days of definitive surgical resection including complete lymphadenectomy, the doses used are 6mcg/kg/week subcutaneous for 8 doses, then 3 mcg/kg/week SC for up to 5 yr. Rotating the injection sites.

-Phase I study in patients with neurofibromatosis related plexiform neurofibromas had a recommended dose for phase II of 1mcg/kg/week. [17]

-The doses used for the patients treated in the series with recurrent craniopharyngioma ranged from 1 to 3 mcg/kg/dose.

-For this trial, **the dose is 1 mcg/kg/dose**. There are specific criteria for reduction of the dose based on toxicity. Two dose modifications have been permitted.

2.8 Imaging

Imaging of the tumor will be assessed with MRI of brain and /or spine with and without contrast performed on a 1.5 or 3T scanner. Progressive disease will be defined on the basis of a comparison of the baseline scan to the scan demonstrating best response. All axial images should be obtained in a plane parallel to a line intersecting the bottom of the genu and of the splenium of the corpus callosum to assure consistency of imaging plane. Coronal images should be obtained in a plane perpendicular to the axial images.

- 1) Axial diffusion tensor imaging whole brain
- 2) Sagittal, volumetric T1-weighted, gradient echo whole head
- 3) Axial T2-weighted fast spin echo (FSE) whole head
- 4) 3D Coronal FLAIR.
- 5) Coronal T2-weighted fast spin echo (FSE), fat saturated through the orbits and chiasm.
- 6) Axial T2-weighted fast spin echo (FSE), fat saturated through the orbits and chiasm.
- 7) Axial volumetric T1-weighted gradient echo post contrast whole brain.
- 8) Axial Oblique T1-weighted Fat Suppressed gradient echo post contrast, optic nerves and chiasm.
- 9) Coronal T1-weighted Fat suppressed gradient echo post contrast, optic nerves and chiasm. If imaging of the spine is needed, axial and sagittal T2 and post contrast T1 weighted images will be acquired. Diffusion images of the spine will be obtained if clinically indicated. Volumetric studies for MRI of the brain will be obtain to better evaluate the cystic component of the Low grade gliomas and be able to evaluate responses to the therapy. These sequences are the minimum required to evaluate the response to the treatment. Additional sequences such as MR spectroscopy can be obtained if clinically indicated per institutional protocols.

3.0 STUDY ENROLLMENT PROCEDURES AND PATIENT ELIGIBILITY

3.1 Study Enrollment

3.1.1 Patient registration

Patients may be enrolled on the study once all eligibility requirements for the study have been met. Patients who give informed consent for the protocol in order to undergo screening for eligibility are not considered enrolled and should not be enrolled until the screening is completed and they are determined to meet all eligibility criteria. A registration packet is available from the study coordinator to assist with registration requirements for this protocol. The Aflac Cancer Center CRO will provide electronic confirmation of registration and a study number will be assigned to the patient prior to begin treatment. The study number will be used to identify the patient in all future communications/interactions. An email confirming eligibility will be sent to the Study PI, and Co-PI. The date protocol therapy is projected to start must be no later than 14 calendar days after the date of study enrollment. **Patients must not receive any protocol therapy prior to enrollment.**

3.1.2 IRB Approval

Emory IRB approval of this study is to be provided to the Aflac CRO prior to any patient enrollment.

3.1.3 Reservation and Contact Requirements

Investigators should refer to the Emory IRB website to determine if the study is currently open for accrual and listed as active. Before enrolling a patient on study, a reservation must be made at the Aflac CRO.

Patients must be enrolled within 14 calendar days of making a reservation.

Eligible patients can make a reservation by contacting the Clinical Research Office, Monday through Friday, 8:00 am-4:30 pm Eastern Standard Time at [contact] (phone) except holidays. Calls will be returned within one business day. The appropriate research coordinator will review preliminary eligibility by phone before forwarding a registration packet. The information requested in the registration packet must be completed. The signed informed consent statement along with the documentation confirming eligibility must be faxed to [contact]. Upon receipt of the completed registration packet, the research coordinator at Children's Healthcare of Atlanta will assign a unique study subject number.

3.1.4 Timelines Summary

All pre-treatment evaluations should be performed within **14 days** prior to enrollment and **30 days** for baseline MRI brain and/or spine. From the reservation to enrollment a maximum of 14 calendar days. From enrollment to start therapy maximum 14 calendar days. Patients must not receive any protocol therapy prior to enrollment.

3.1.5 Informed Consent/Assent

The investigational nature and objectives of the trial, the procedures and treatments involved and their attendant risks and discomforts, and potential alternative therapies will be carefully explained to the patient or the patient's parents or guardian if the patient is a child, and a signed informed consent and assent will be obtained according to institutional guidelines.

3.1.6 Screening Procedures

Diagnostic or laboratory studies performed exclusively to determine eligibility for this trial must only be done after obtaining written informed consent. Documentation of the informed consent for screening will be maintained in the patient's research chart. Studies or procedures that were performed for clinical indications (not exclusively to determine eligibility) may be used for baseline values even if the studies were done before informed consent was obtained.

3.1.7 Eligibility Checklist

Before the patient can be enrolled, the responsible institutional investigator must sign and date the completed eligibility checklist. A signed copy of the checklist will be faxed immediately following enrollment to the Aflac Cancer Center CRO at [contact].

3.2 Eligibility Criteria

All clinical and laboratory studies to determine eligibility must be performed within **14 days** prior to enrollment, except MRI brain and/or spine within **30 days** prior to enrollment. If more than 14 calendar days elapse between the date eligibility studies were obtained and the start date of treatment, then the following studies must be repeated prior to treatment: CBC with differential, bilirubin, ALT (SGPT) and serum creatinine. If any of these repeat laboratory studies are outside the parameters required for eligibility (labs may again be repeated within 48-72 hours), then the patient is off protocol therapy. Imaging studies are required within **30 days** prior to enrollment.

Important note: The eligibility criteria listed below are interpreted literally and cannot be waived. All clinical and laboratory data required for determining eligibility of a patient enrolled on this trial must be available in the patient's medical or research record which will serve as the source document for verification at the time of audit.

3.2 INCLUSION CRITERIA

3.2.1 Age

Patients must be older than 3 years and less than or equal to 25 years of age at the time of enrollment

3.2.2 Neurofibromatosis

Patients with neurofibromatosis are eligible.

3.2.3 Diagnosis

Histologic confirmation is not required for this if the patient has NF-1 with MRI findings consistent with optic pathway glioma or JPA. Any other tumors will need histological confirmation, either at the time of diagnosis or at the time of recurrence. The histological diagnosis includes WHO grade I JPA.

3.2.4 Measurable Disease

Patients must have measurable residual disease, defined as tumor that is measurable in two or three perpendicular diameters on MRI. For a lesion to be considered measurable, it must be at least twice the slice thickness on MRI (i.e visible on more than one slice)

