9.2 Study Design

The study is designed using Simon's two stage optimal design with a power of 80% and an alpha error of 5%. We assume an uninterested response rate of 5% and the promising response rate is 25%. In the first stage of the study, 9 eligible patients will be enrolled. If none responder among the 9 patients, the study terminates and treatment will be determined to have no improvement in the response rate. Otherwise, the study will continue with the second stage in which 8 additional eligible patients will be enrolled for a total of 17 eligible patients. At the end of total patient accrual, at least 3 of 17 eligible patients must

achieve response in order to consider the treatment interesting for further evaluation. Response is considered as either CR or PR or SD.

Optimal Two Stage Design	Optimum Design
First Stage Sample Size (n1)	9
Upper Limit For 1st Stage Rejection of Drug (r1)	0
Maximum Sample Size (n)	17
Upper Limit for 2nd Stage Rejection of Drug (r)	2
Expected Sample Size If Response Probability = P0	11.96
Probability of Early Termination at P0	0.63

9.3 Methods of Analysis:

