9.4 Analysis of Efficacy

Each patient will be classified according to their 'best response' for the purposes of analysis of treatment effect. A responder is defined as a patient who achieves a best overall response of CR or PR at any time on the study. If a patient achieves a PR or CR and later has progressive disease or relapse, then the patient will be counted as a responder. The response rate will be calculated as the ratio of the number of patients who demonstrate response (CR or PR) divided by the number of patients evaluable for response. All patients eligible for study who receive any study drug will be considered evaluable for response. Any patient who goes off protocol therapy for any reason (patient/parent/physician choice, adverse event profile, etc.) prior to the first response evaluation will be considered a non-responder. Disease progression will be based on the results of institutional review. Standard survival methods will be used for analysis of EFS and OS. Analyses include log rank tests and the product-limit (Kaplan-Meier) estimate for estimation of EFS and OS probability.

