1. The amount of tumor enhancement is quite variable in LGGs from one scan to the next. Therefore, tumor response/progression will not solely be determined by change in the amount of enhancing disease on post contrast T1 images. Measurable change in size/extent must be present on FLAIR/T2 images, or on pre-contrast T1 images.

2. Development of new disease or progression in any established lesions is considered progressive disease, regardless of response in other lesions – e.g. when multiple lesions show opposite responses, the progressive disease takes precedence.

Note:

- CT scans should not be used to determine response. For MRI imaging, the longest diameter can be measured from the axial plane or the plane in which the tumor is best seen or measured, provided the same plane and MR sequence is used in follow ups.
- The cystic components of a tumor are considered in separate tumor measurements. See options below.

Options:

- If the cyst/necrosis is eccentric, the W, T and L of the solid portion should be measured, the cyst/necrosis excluded from measurement.
- If the cyst/necrosis is central but represents a small portion of the tumor (<25%), disregard and measure the whole lesion.
- If the cyst/necrosis is central but represents a large portion of the tumor, identify a solid aspect of the mass that can be reproducibly measured.
- Leptomeningeal tumor spread is usually not a target lesion, and usually cannot be measured accurately. Presence and location of leptomeningeal tumor spread should be noted, change in extent/thickness assessed on follow up studies.
- For patients with large cystic components (>25%): One cystic component should be identified in the baseline scan. It should be measured separately from the solid component. It should be measured in 3 dimensions in the best sequence likely the T2 sequences. (L x T x W).

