Appendix 3: Eligibility Checklist

A Phase II Study Of Pegylated Interferon Alfa-2b In Children With Refractory/ Recurrent juvenile pylocytic astrocytomas or optic gliomas.

Last Name: _____ First Name: _____ MI: _____ ID #: _____
Date of Birth: _____ (mm/dd/yyyy)

Age: _____ Race: _____ (White, Hispanic, Black, Asian, Other)

To be eligible, questions 1-10 must be marked Y (Yes) or NA (Not Applicable), and questions 11-14 must be marked N (No).

1. Is the patient older than 3 years and less than or equal to 25 years of age? _____

2. Has the patient been diagnosed with an optic pathway glioma or JPA? _____

a. Is there radiographic evidence of optic pathway glioma or JPA? _____

3. Has the patient received 5 or fewer chemotherapy regimens? _____

4. Does the patient have a performance status of more than 50? _____

5. Does the patient have an adequate bone marrow function as defined below?

-peripheral absolute granulocyte count of $>1000/\text{mm}^3$, _____

-hemoglobin $>8 \text{ gm/dL}$ _____ (transfusion dependent)

-platelet count $>100,000/\text{mm}^3$ _____ (transfusion independent)

6. Does the patient have adequate hepatic function (total bilirubin $<2.0x$ the upper limit of normal and direct bilirubin within normal limits and SGPT $<2.5 x$ the upper limit of normal) or for patients with a diagnosis of Gilbert's disease an indirect bilirubin of $< 6\text{mg/dl}$ and a direct bilirubin of $< .5\text{mg/dl}$? _____

7. Have one of the following two criteria for renal function been met? _____

a. Creatinine clearance $=60 \text{ mL/min/1.73 m}^2$

b. Maximum age-adjusted normal serum creatinine?

i. Five years of age or younger: 0.8 mg/dl

ii. Ten years of age or younger, but must be greater than five years of age: 1.0 mg/dl

iii. Fifteen years of age or younger, but must be greater than ten years of age: 1.2 mg/dl

iv. Greater than fifteen years of age: 1.5 mg/dl

8. Has the patient, their legal guardian, or a Durable Power of Attorney (for those patients 18 to 21 years of age) signed a document of informed consent? _____

9 Does the patient have evidence of measurable disease in brain MRI? _____

10. Has the patient received prior radiation more than 24 months ago? _____
11. Is the patient currently receiving other investigational chemotherapeutic agents? _____
12. Does the patient have any known hypersensitivity to interferon alpha? _____
13. Is the patient pregnant or breast-feeding? _____

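### The measurable-disease criterion (3.2.4, checklist item 9) names no MR sequence, whereas 10.4 item 1 calls response or progression only with measurable change on FLAIR/T2 or pre-contrast T1, so entry and scoring should be aligned.

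*Combined protocol and SAP*

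**What the plan says.** All references are to the combined protocol and SAP.

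- **Entry.** Section 3.2.4: "Patients must have measurable residual disease, defined as tumor that is measurable in two or three perpendicular diameters on MRI". It adds a minimum size of twice the slice thickness but no sequence. Item 9 of the Appendix 3 checklist asks only: "Does the patient have evidence of measurable disease in brain MRI". Section 3.2 says that the criteria are to be read literally and not waived.
- **Scoring.** Section 10.4 item 1 notes that enhancement in these tumours varies between scans, so a change in enhancement on post-contrast T1 cannot by itself decide response or progression. It continues: "Measurable change in size/extent must be present on FLAIR/T2 images, or on pre-contrast T1 images".
- **Follow-up sequence.** A note in 10.4 allows the plane in which the tumour is best seen, on condition that plane and sequence stay the same at follow-up.
- **Denominator.** Section 9.4: "All patients eligible for study who receive any study drug will be considered evaluable for response". It defines a responder as a patient with CR or PR.
- **Decision rule.** Section 9.2 sets an optimal Simon two-stage design with 5% and 25% as the uninteresting and promising rates, 80% power and 5% alpha. At stage 1: "If none responder among the 9 patients, the study terminates". At the end, "at least 3 of 17 eligible patients must" respond. The same section also says that SD counts as response, which conflicts with 1.1 and 9.4.

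**The concern.** The scoring rule is narrower than the entry rule. Read literally, a lesion whose diameters can be measured only on post-contrast T1 satisfies 3.2.4. Such a child would then be followed on the one sequence that 10.4 item 1 treats as insufficient alone. With no measurable extent on FLAIR/T2 or pre-contrast T1, it is hard to see how measurable change there could be shown, so CR, PR and size-based PD would probably be out of reach. Clinical progression, new lesions and progression of non-target lesions would remain possible. Nothing in the plan excludes, replaces or separately handles this child, who therefore stays in the denominator.

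In a 17-patient trial decided on three responders, even one result fixed by the scoring rule rather than by the drug may matter. Under CR/PR it pushes towards wrongly dropping the drug. Such a child could also fail on EFS only by routes other than growth of the target lesion; the documents give no basis for sizing that effect.

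**Working it through.** **Inputs from 9.2 and 9.5.** n1 = 9, stop if 0 responders; n = 17, success if at least 3; p0 = 0.05; p1 = 0.25.

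**1. Reproduce the plan.** Let b(x; m, p) be the binomial probability of x responders in m patients.

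- Early termination at p0: 0.95^9 = 0.6302 (plan: 0.63).
- Expected sample size at p0: 9 + (1 − 0.6302) × 8 = 11.96 (plan: 11.96).
- Probability of success = sum over x ≥ 1 of b(x; 9, p) × P(Bin(8, p) ≥ 3 − x).
- At p = 0.25: 0.2253 × 0.6329 + 0.3003 × 0.8999 + 0.3993 = 0.1426 + 0.2703 + 0.3993 = 0.812, so power is 81.2%.
- At p = 0.05 the same sum gives an alpha of 4.66%.

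The design is reproduced. Its margin over 80% is 1.2 points.

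**2. Assume k of the 17 cannot be scored CR or PR, and 25% applies to the others.** The documents do not give k; 0 to 3 is an assumed range. With k1 such children in stage 1 and k2 in stage 2, replace 9 by 9 − k1 and 8 by 8 − k2 in the sum.

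For k = 1 in stage 1: 0.2670 × 0.6329 + 0.3115 × 0.8999 + 0.3215 = 77.1%. In stage 2 the result is 78.5%. Weighted by the chance of each placement: 9/17 × 77.07 + 8/17 × 78.46 = 77.7%.

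| k of 17 | Power, random placement | Range over placements | Alpha, range over placements |
|---|---|---|---|
| 0 | 81.2% | – | 4.66% |
| 1 | 77.7% | 77.1–78.5% | 3.9–4.1% |
| 2 | 73.7% | 72.1–75.1% | 3.2–3.5% |
| 3 | 69.1% | 66.2–71.1% | 2.6–2.9% |

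The alpha column holds the other patients at 5%. The chance of stopping at stage 1 when scorable patients respond at 25% is 0.75^(9 − k1): 7.5%, 10.0%, 13.3% and 17.8% with 0, 1, 2 and 3 such children among the first nine.

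**3. Assume instead that 25% is the rate over all 17.** Scorable patients must then respond at 0.25 × 17/(17 − k), that is 26.6%, 28.3% and 30.4% for k = 1, 2 and 3. Power averaged over placement is 81.5%, 81.8% and 82.1%. There is no average loss.

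The loss in step 2 therefore depends on both the assumed k and the reading of the 25%.

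**The case against.** Four counter-arguments carry weight.

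1. **Such a child is not strictly barred from response.** Item 1 of 10.4 asks for measurable change in size or extent on any one of several sequences. It does not say that baseline diameters must have been measurable there. A lesion with a blurred T2 margin might still show a change in extent. A reader might infer that every such child is a certain non-responder; the text supports only that CR or PR is improbable.
2. **Other sections already steer target choice.** Section 10.6 asks for targets that can be measured accurately and repeatedly, and 10.4 warns that enhancement varies. Objective 1.2.3 and section 9.10 presuppose assessment on T2, FLAIR and post-contrast T1 alike. This makes an enhancement-only target less likely, but none of it amends 3.2.4 or the checklist.
3. **There may be no such patients.** Section 2.1 says that these tumours usually enhance, which says nothing about whether they can be measured on T2/FLAIR. Leptomeningeal spread, one candidate, is described in 10.4 as usually not a target.
4. **The power loss depends on the estimand.** Section 9.4 defines the rate over all evaluable patients, and 9.2 does not restrict the 25% to scorable ones. A reader might infer that one such child takes the trial below its stated power. That follows only under step 2 of the working, not under step 3.

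The direction is also conditional. Under the 9.2 sentence counting SD as response, a child who can be scored neither PR nor size-based PD would tend to default to SD and count as a responder. One automatic responder, with 5% in the others, would raise the false-positive rate from 4.7% to 16.1% (in stage 2) or 18.9% (in stage 1). That conflict is a separate point. It does not remove the mismatch, because on either definition the scoring rule rather than the drug would largely settle the child's result.

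**Conclusion.** The mismatch between entry and scoring is in the text and worth closing. Sections 3.2.4 and checklist item 9 leave the sequence open, 10.4 item 1 does not, and 9.4 keeps every eligible treated patient in the count.

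Its practical size is unknown and may be zero. The illustrative fall from 81.2% to 77.7%, 73.7% or 69.1% rests on three assumptions: one to three such children among 17, 25% as the rate among scorable patients, and response meaning CR or PR. Alpha falls as well, so under these assumptions the error runs only towards rejecting an active drug. The documents do not show that the design is underpowered. This is an inexpensive wording alignment, and the Simon calculation itself is correct.

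**What to change.** In 3.2.4 and checklist item 9, require at least one target lesion to be measurable at baseline on T2/FLAIR or pre-contrast T1, the sequences on which 10.4 item 1 allows change to be called. Record the qualifying sequence on the checklist.

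The cost is one phrase in each place and one recorded item. No scan is added for brain lesions, since 2.8 already acquires T2, FLAIR and pre-contrast T1. The downside is that any patient measurable only by enhancement would not be enrolled.

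Separately, reconcile the responder definition in 9.2 with 1.1 and 9.4, because the direction of this effect depends on it.
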